8.4 Statistical Analysis Plan

8.4.1 Analysis of Demographic and Baseline Characteristics

Descriptive statistics (mean, standard deviation, median, minimum and maximum) for age, height, weight, BMI and comorbidity score at enrolment will be calculated overall and by vaccine group.

Distributions of subjects by sex, age, ethnic origin (race, ethnicity), previous vaccination status, smoking status, comorbidity and risk of complications from influenza will be summarized overall, by vaccine group, and by age group and vaccine group.

8.4.2 Analysis of Primary Objective(s)

8.4.2.1 Analysis of Primary Safety Objective(s)

8.4.2.1.1 Analysis of Extent of Exposure

The number of subjects actually receiving the vaccination will be summarized by vaccine group.

8.4.2.1.2 Analysis of Solicited Local, Systemic and Other Adverse Events

Solicited local AEs include: injection site erythema, induration, ecchymosis and pain.

Solicited systemic AEs include: loss of appetite, nausea, fatigue, generalized myalgia, generalized arthralgia, headache, chills, vomiting, diarrhea.

All solicited adverse events will be summarized according to defined severity grading scales.

Frequencies and percentages of subjects experiencing each adverse event will be presented for each symptom severity. Summary tables showing the occurrence of any local or systemic adverse event overall and at each time point will also be presented.

Post-vaccination solicited adverse events reported from day 1 to Day 7 will be summarized for the intervals Day 1-3, Day 4-7, Day 1-7 by maximal severity and by vaccine group, excluding the 30 minute measurement, which will be summarized separately. Injection-site erythema, ecchymosis and induration will be summarized according to categories based on linear measurements, please refer to the SAP for definition of categories.

Injection site pain and systemic adverse events (except fever) occurring up to 7 days after each vaccination will be summarized according to “mild”, “moderate” or “severe” categorization. For the definition of severity grades please refer to the [Section 7.1.1](#) of the protocol.

Each solicited local and systemic adverse event will also be further summarized as “none” versus “any”. “Any” will include reactions with a diameter of at least 1 mm.

Implausible measurements (for further definition see SAP) will be left out of the analysis.

Use of antipyretics and analgesics will be summarized by frequency and percentage of subjects reporting use. Summaries by type of use (prophylactic versus treatment) and by treatment arm will be provided.

Body temperature will be summarized by 0.5 °C and 1.0 °C increments from 36.0 °C up to ≥ 40 °C and will be broken down according to route of measurement. In addition, fever will be summarized according to “mild”, “moderate” or “severe” categorization. For the definition of severity grades please refer to the SAP.

8.4.2.1.3 Analysis of Unsolicited Adverse Events

This analysis applies to all adverse events occurring during the study, judged either as probably related, possibly related, or not related to vaccination by the investigator, recorded in AE CRF, with a start date on or after the date of first vaccination. AE starting prior to the first vaccination will only be listed. The original verbatim terms used by investigators to identify adverse events in the CRFs will be mapped to preferred terms using the Medical Dictionary for Regulatory Activities (MedDRA) dictionary. The adverse events will then be grouped by MedDRA preferred terms into frequency tables according to system organ class (SOC).

All reported adverse events, as well as adverse events judged by the investigator as at least possibly related to study vaccine, will be summarized according to SOC and preferred term within SOC. These summaries will be presented by vaccination group and by interval of study observation. When an adverse event occurs more than once for a

subject, the maximal severity and strongest relationship to the vaccine group will be counted.

Separate summaries will be produced for the following categories:

- SAE;
- Adverse events that are possibly or probably related to vaccine;
- Medically attended adverse events that occur within 30 days following RT-PCR confirmed ILI
- AESI;
- NOCD;
- Adverse event leading to withdrawal;
- Adverse event resulting in death.

Data listings of all adverse events will be provided by subject. In addition, adverse events in the categories above will be provided as listed data.

For **handling of missing data** the entire study period will be divided into disjoint intervals based upon the time and event schedule in the protocol:

Solicited AEs: 30 min, 6h-Day 3, Day 4-Day 7, and one overall interval: 6h-Day 7.

Unsolicited AEs: [Day 1-22], [Day 23-181], [Day 182-366], and [Day 1-366].

No imputation of missing solicited or unsolicited AEs will be used. The percentage of subjects with missing solicited AE assessments (e.g. missing Patient Diary) and missing Safety Phone Call or safety assessment will be reported for each time period.

8.4.2.1.4 Analysis of Safety Laboratory Values

Not applicable.

8.4.2.2 Analysis of Primary Efficacy Objective(s)

8.4.2.2.1 Statistical Hypotheses

The primary absolute efficacy objective will be evaluated using following null (H_0) and alternative (H_1) hypotheses:

$$H_0: 1 - HR = VE \leq 0.4 \quad \text{versus} \quad H_1: VE > 0.4,$$

where HR is a hazard ratio of aQIV versus non-influenza comparator.

8.4.2.2.2 Analysis Sets

Primary vaccine efficacy analyses will be based on the Efficacy FAS, and repeated on the Efficacy PPS.

8.4.2.2.3 Statistical Methods

Cox Proportional Hazards (PH) model will be used to estimate the hazard ratio:

$$HR = \lambda_{aQIV}(t) / \lambda_{Comp}(t) = \exp(\beta_g (x_{ig} - x_{jg}) + \beta_a (x_{ia} - x_{ja}) + \beta_c (x_{ic} - x_{jc})),$$

where $\lambda_{aQIV(s)}(t)$ and $\lambda_{Comp(s)}(t)$ are stratum-specific hazards at time t, for stratum s that reflects a combination of age group (<75 vs ≥ 75 years) and low vs high (score <50 vs ≥ 50) risk of influenza complications, in aQIV and comparator group, respectively; β_g denotes regression coefficient and $x_{ig(s)}$, $x_{jg(s)}$ are indicators of treatment group for individuals i and j within stratum Subjects that did not experience ILI during observation period and subjects that dropped out from the study during observational period will be censored (right-censoring). The estimate of the hazard ratio, the respective estimate for absolute VE and pertaining 2-sided 95% CIs will be calculated based on this model. If the study continues over several seasons, estimates will be also adjusted for the factor season (s). Factor site/center or country might be added to the model if appropriate. In case of more than one interim analysis confidence level for the estimates at the final stage will be adjusted.

Estimates for hazard ratio in the PH model will be calculated using Maximum Partial Likelihood (MPL) method. In case of problems with convergence (algorithm does not converge or converges to infinite estimates) penalized ML approach will be used ([Heinze and Schemper, 2001](#)).

In case interim analyses will be performed a k-stages group - sequential test procedure for time-to-event data will be implemented. As the K-stage interim analysis for relative vaccine efficacy introduces a multiple test problem, alpha will be adjusted using error-spending function as described in [Section 8.6](#). For this group sequential test procedure parameters like information level and/or standard error at each stage will be calculated by the above described model and then used to calculate the actual group sequential test that compared the test statistic at each stage with the respective boundaries. Repeated CIs for each stage and also the final estimator and the respective CI can be retrieved by the group sequential test method to maintain simultaneous coverage probability ([Jennison, 2000](#)).

Further details of the statistical methods will be provided in the SAP.

Missing immunogenicity values are considered missing completely at random (MCAR) and therefore will not contain information that impact the result of the analysis (i.e., not informative). Imputation methods will therefore not be used. The secondary objectives will be analyzed using the FAS (immunogenicity). If the percentage of vaccinated subject excluded from the FAS (immunogenicity) is greater than 5%, a secondary analysis based on the PPS will be performed to complement the FAS.

Efficacy data will be analyzed using both the FAS (Efficacy) and the PPS, irrespective of the difference in size between the two analysis sets.

The following algorithm will be applied:

1. If less than 20% of subjects are without efficacy data (e.g., ILI swabs collected without any RT-PCR assessment record), then the analyses will be run on FAS and PPS and no further statistical evaluation will be performed.
2. If observations are missing for 20% or more of subjects, the missing mechanism will be analyzed with vaccine group as a categorical variable and a newly created variable describing the missing information as dependent variable (1=efficacy record present; 0=efficacy record not present). It will be tested, by chi-square test, if the proportion of missing observations/subjects varies significantly between vaccine groups. If the difference is significant with $P < 0.05$ then a sensitivity analysis will be performed of the primary efficacy analysis imputing randomly x% (from 0% to 100% in 10% increments) of missing data as PCR-confirmed cases.

8.4.2.3 Analysis Of Primary Immunogenicity Objective(S)

There are no primary immunogenicity objectives in this study.

8.4.2.3.1 Statistical Hypotheses

Not applicable.

8.4.2.3.2 Analysis Sets

Not applicable.

8.4.2.3.3 Statistical Methods

Not applicable.

8.4.3 Analysis of Secondary Objective(s)

8.4.3.1 Analysis of Secondary Safety Objective(s)

There are no secondary safety objectives in this study.

8.4.3.1.1 Analysis of Extent of Exposure

Not applicable.

8.4.3.1.2 Analysis of Solicited Local, Systemic and Other Adverse Events

Not applicable.

8.4.3.1.3 Analysis of Unsolicited Adverse Events

Not applicable.

8.4.3.1.4 Statistical Hypotheses

Not applicable.

8.4.3.1.5 Analysis Sets

Not applicable.

8.4.3.1.6 Statistical Methods

Not applicable.

8.4.3.2 Analysis of Secondary Efficacy Objective(s)

8.4.3.2.1 Statistical Hypotheses

Hypotheses for testing key secondary objective are formulated in the similar way as for the primary efficacy objective. Other secondary efficacy objectives are not associated with any hypothesis testing.

8.4.3.2.2 Analysis Sets

All secondary efficacy objectives will be evaluated based on the Efficacy FAS, and analysis for the key secondary objective will be also repeated based on Efficacy PPS.

8.4.3.2.3 Statistical Methods

Similarly to the primary efficacy objectives, the PH model will be used to estimate absolute vaccine efficacy for secondary objectives 1-4. Evaluation of the key secondary objective will be done according to the conditional testing procedure. Absolute efficacy of aQIV with respect to the culture confirmed matched influenza will be demonstrated only providing successful demonstration of the primary objective (absolute efficacy with respect to RT-PCR-confirmed influenza regardless of antigenic match). This conditioning allows testing of both primary and key secondary efficacy objectives on the same significance level alpha.

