8.2.2.2 Success Criteria for Secondary Efficacy Objective(s)

The key secondary objective is achieved if the lower-limit (LL) of the two-sided 95% CI of absolute vaccine efficacy estimate is > 0.4 . As for the primary efficacy objective, the CI confidence level will be adjusted to reflect adjustment of type 1 error (alpha) in case of more than one interim analysis.

Other secondary efficacy/effectiveness objectives will not be tested for success.

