8.5 Sample Size and Power Considerations of Primary and Secondary Objectives

Efficacy objectives:

Sample size and power consideration for the aQIV efficacy objective is based on criteria for demonstrating efficacy in placebo controlled studies provided in CBER guidance, specifically that the study should be powered to assess the lower bound of the two-sided 95% CI of vaccine effectiveness, anticipated to be substantially above zero. This study is planned using a group sequential design. The power of Cox Regression which is planned to be used for analysis is dependent on the overall number of influenza cases, so the sample sizes on number of subjects described in this section is provided more for operational reasons. Additional information on the planning of number of subjects that may need to be enroled if it is decided to continue enrolment after interim analyses is described in [Section 8.6](#).

For the primary efficacy objective: with 1-sided alpha of 2.5% and assuming an attack rate of influenza of 3.5% among subjects enroled in the non-influenza comparator group and 1.4% among the aQIV group, i.e. 60% assumed vaccine efficacy for aQIV, 238 events (i.e. 4,860 subjects per group under the assumed ERs) are needed with 86.5% power to show the absolute efficacy of aQIV versus non-influenza comparator, in preventing first occurrence RT-PCR-confirmed influenza A and/or B, due to any strain of influenza regardless of antigenic match to the strains in aQIV, in subjects ≥ 65 years of age, using a margin of 40% for lower bound of the CI for absolute vaccine efficacy.

For the first secondary efficacy objective: with a group vaccine efficacy of 65% but expecting conservatively reduced event rates of influenza cases due to matched strains of 2.5% among subjects in the non-influenza comparator group and 0.9% among the aQIV group then 144 events has estimated power approximately 88.5% to show the absolute efficacy of aQIV versus non-influenza comparator, using a margin of 40% for lower bound of the CI.

Assuming a drop-out rate of 10%, approximately 10,692 subjects \geq 65 years, 5,346 per vaccine group will be randomized to receive either aQIV or non-influenza comparator (Boostrix®) in a 1:1 allocation ratio, stratifying by age (\geq 65 to 74 and \geq 75 years of age), study site and by low vs high risk of influenza complications (score <50 vs \geq 50).

Immunogenicity objective:

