12.2 Secondary Objectives Analysis

Hypotheses for testing secondary objectives are formulated in the similar way as for the primary efficacy objective. If an interim analysis is performed and the trial doesn't stop, then all the subsequent secondary analysis will be tested at a reduced alpha level, i.e. what's left from the interim analysis. The confidence interval will be higher than 95% instead of 95% at the final analysis.

All secondary efficacy objectives will be evaluated based on the Efficacy FAS, but analysis for the key secondary objective will be also repeated based on Efficacy PPS. For non-key secondary objectives, if the percentage of vaccinated subject excluded from the FAS is greater than 5%, a secondary analysis based on the PPS will be performed to complement the FAS.

Similarly to the primary efficacy objectives, a Cox PH model will be used to estimate absolute vaccine efficacy VE for each secondary objective 1-4.

Criteria for evaluation : if the lower limit of the 95% two-sided confidence interval for VE estimate is greater than 40% then the secondary efficacy objectives will be demonstrated.

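### If the trial stops early for efficacy, neither document adjusts the key secondary's 95% interval, so gating alone does not hold its one-sided error at 2.5% (worst case about 3.1–3.2% with an interim at half the cases)

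*Protocol*

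**What the plan says.** - **Gate.** Protocol 8.4.3.2.3 makes the key secondary conditional on primary success and adds: "This conditioning allows testing of both primary and key secondary efficacy objectives on the same significance level alpha".
- **Key secondary criterion, protocol.** Section 8.2.2.2 requires the lower limit of a two-sided 95% interval to exceed 0.4. It says that, as for the primary, "the CI confidence level will be adjusted to reflect adjustment of type 1 error (alpha) in case of more than one interim analysis".
- **Key secondary criterion, SAP.** Section 12.2 reduces the secondary alpha when an interim has been done and the trial continues. The criterion it states is "if the lower limit of the 95% two-sided confidence interval for VE estimate is greater than 40" (per cent).
- **Primary.** Protocol 8.6 and SAP 14.1 give it explicit stage boundaries. The worked example has one-sided p below 0.00625 at 119 cases and 0.02275 at 238, with futility above 0.35022 at the interim.
- **Multiplicity in general.** SAP 8.4 applies an error-spending function at each stage of the group-sequential design. It does not mention the key secondary.

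No section gives a boundary for the key secondary at an interim.

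**The concern.** Fixed-sequence testing protects the second hypothesis when everything is tested at one analysis. Here the primary can open the gate at the interim or at the final. When primary VE is well above 40%, the gate mainly decides when the key secondary is tested and gives it little protection. If it is then judged at Z = 1.96 after a first-interim stop, and at about 1.96–2.00 when the trial runs on, the chances of a false claim on the two routes add up.

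The key secondary is the only secondary efficacy objective that the protocol tests formally (8.4.3.2.1), and the data are meant to support licensure (Protocol 1.1). A matched-strain claim after an early stop could rest on about half the planned cases, at a level the plan does not actually control.

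**Working it through.** **Inputs from the documents**
- Protocol 8.5: "with 1-sided alpha of 2.5% and assuming an attack rate of influenza of 3.5" per cent; "i.e. 60% assumed vaccine efficacy for aQIV"; "238 events (i.e. 4,860 subjects per group under the assumed ERs) are needed with 86.5% power"; "then 144 events has estimated power approximately 88.5% to show the absolute efficacy"; allocation "in a 1:1 allocation ratio, stratifying by age".
- Protocol Table 8.6-1 (SAP Table 1): interim at 119/238, so t = 0.5. Boundaries 0.00625 (Z = 2.498) and 0.02275 (Z = 2.000).
- The O'Brien-Fleming-type spending function named in Protocol 8.6 gives 0.00153 (Z = 2.963) at t = 0.5, then 0.0245 (Z = 1.969). This differs from the table, so both sets are carried through.

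**Assumptions not in the documents**
- Matched cases are a subset of the primary cases, so the two statistics have correlation ρ = √(144/238) = 0.78. Other values are shown.
- The key secondary is also at half information at the interim (72 of 144 cases).
- Futility is non-binding unless stated.

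**1. Reproducing the plan.** Primary drift = √(238/4) × ln(0.60/0.40) = 7.714 × 0.4055 = 3.13. Fixed-design power = Φ(3.13 − 1.96) = 87.9%. With the table's two stages and binding futility it is 86.5%, as stated. Given 0.00625 and binding futility at 0.35022, the final boundary comes out at 0.02275, as stated. For the key secondary, √(144/4) × ln(0.60/0.35) = 6 × 0.539 = 3.23, giving 89.9% at Z = 1.96 and 89.1% at Z = 2.00, close to the stated 88.5%.

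**2. Key secondary error.** With primary boundaries a1, a2, key secondary critical values c1, c2, and matched VE exactly 40%:

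error = P(Zp1 > a1, Zs1 > c1) + P(Zp1 ≤ a1, Zp2 > a2, Zs2 > c2)

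The stage correlation is √0.5. The error is evaluated by multivariate-normal integration and maximised over the primary drift. As written, c1 = 1.96, and c2 is either the reduced value or 1.96.

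| ρ | As written | Key secondary on O'Brien-Fleming boundaries | Key secondary on Table 8.6-1 boundaries |
|---|---|---|---|
| 0.50 | 2.7–2.9% | 1.8% | 1.6% |
| 0.78 | 3.1–3.2% | 2.0% | 1.9% |
| 0.90 | 3.3–3.5% | 2.2% | 2.1% |
| near 1 | 3.9–4.1% | 2.5% | 2.6% |

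The ranges cover both primary boundary sets and both choices of c2. Example at ρ = 0.78 with the table boundaries, drift 1.85 and c2 = 2.00: 2.06% through the interim route plus 1.01% through the final route, about 3.06%. The maxima fall at an overall VE of about 52–56%. Using 1.96 at both looks with the gate always open gives the ceiling, 4.16%.

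**3. Dependence on primary VE (ρ = 0.78, t = 0.5).** At primary VE 40% the error is 1.1–1.2%; at the planned 60% it is 2.7–2.8% with the table boundaries and 3.0% with O'Brien-Fleming.

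**4. Dependence on interim timing (ρ = 0.78, final level adjusted).** The maximum is 2.8–3.0% at t = 0.6, 2.6–2.8% at t = 0.7 and 2.5–2.6% at t = 0.8.

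**5. Chance of an early stop at planned VE 60%.** The interim drift is √(119/4) × 0.4055 = 2.21. The stopping probability is Φ(2.21 − 2.498) = 39% with 0.00625, or Φ(2.21 − 2.963) = 23% with O'Brien-Fleming.

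**The case against.** - **The text may intend the primary's stage level.** Protocol 8.2.1.2 and SAP 12.1 use almost the same conditions for the primary, which nonetheless has a strict interim boundary, and 8.2.2.2 ties the key secondary to the primary. If the same alpha means the primary's level at that stage, the error is essentially controlled. This stands as a possible reading, so the documents do not plainly prescribe an uncorrected test. But the primary's boundary is written out in 8.6 and 14.1, and nothing extends it to the key secondary. What is written is a 95% interval, with the conditions that change it, and a first-interim stop is not among them.
- **There is only one test per trial.** A reader might infer two full 2.5% tests of the key secondary. The documents do not support that: it is tested at the stop or at the final, and SAP 12.2 lowers the level on the second route. The excess comes from adding the two routes over repeated trials, as the calculation does.
- **The case split is unusual.** With 144 of 238 cases matched at VE 40%, overall VE 50% implies about 63% in the remaining cases, and overall 60% implies about 83%. Protocol 8.5 assumes the opposite order (65% matched, 60% overall). This makes the worst case less plausible. It does not rescue the quoted sentence, which is unconditional.
- **Half the cases is itself an assumption.** The interim may fall anywhere from 120 to 237 cases, and no section says the key secondary is tested on the interim snapshot. If it were tested at close-out after an early stop, with more cases, the worst case at ρ = 0.78 would be about 2.7–2.8% at 70% of its information and 2.6–2.7% at 80%.

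**Conclusion.** The sentence in Protocol 8.4.3.2.3 is wrong as written. With an interim at half the information, ρ = 0.78 and matched VE 40%, the key secondary's one-sided error reaches about 3.1–3.2% at worst and 2.7–3.0% at the planned primary VE, against 2.5%. These figures rest on the assumed correlation, on equal information fractions and on reading 8.2.2.2 and SAP 12.2 literally.

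A reader might take 4.1% as the size of the problem. It is only a limit as ρ approaches 1, where the two endpoints share nearly all their cases and there is little room for their VEs to differ. Nor is 3.1–3.2% an expected error: it is a maximum over the primary effect. The primary test is not affected by this point. The gap is modest, but it should be closed before any unblinded interim.

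**What to change.** In Protocol 8.2.2.2 and 8.4.3.2.3 and SAP 12.2, state that at whichever stage the primary boundary is crossed, the key secondary is tested against its own O'Brien-Fleming-type boundary for that stage, with the confidence level to match. Say which data cut is used after an early stop. Replace the same-level sentence in 8.4.3.2.3 accordingly.

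Reusing the Table 8.6-1 boundaries is simpler, but can reach about 2.6% as ρ nears 1 unless futility is binding.

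No subjects or visits are added. The cost is power for the key secondary after an early stop. With 72 matched cases and VE 65%, ignoring the gate and using the expected case split, information is 72 × 0.35/1.35² = 13.83 and drift is 0.539 × √13.83 = 2.00. Power falls from about 52% at Z = 1.96 to 31% at Z = 2.50, and to Φ(2.00 − 2.963) = 17% at the O'Brien-Fleming value. With the cruder events/4 information used in the check above (72/4 = 18, drift 2.29), the same three figures are about 63%, 42% and 25%.
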